Appendix 2 Alcohol Restrictions during the study

The subjects must not drink alcohol at least 24 hours prior to the start of the PSG assessments, as well as during the PSG assessments including the morning after the second PSG assessment, until they leave the center.

On non-PSG nights, the subjects will be instructed to limit alcohol to a maximum of 2 drinks per day.

A drink is defined as:

- A bottle/can of 33 cl/12 ounces of beer (\approx 14 grams alcohol)
- A glass of 10–12 cl/4 ounces of wine (\approx 12 grams alcohol)
- A small glass of 3–4 cl/1 ounce of liquor (\approx 9 grams alcohol)

Appendix 3 Caffeine content of common beverages

The content of caffeine in common caffeine beverages is approximately:

- A standard cup of brewed or restaurant-style coffee contains approximately 150–200 mg caffeine.
- A can of most soda drinks (unless decaffeinated soda drinks) contains approximately 50 mg caffeine.
- A can of energy drinks contains approximately 150–200 mg caffeine.

Appendix 4 Forbidden and restricted concomitant medications

1. Forbidden (F) or restricted (R) concomitant medications due to CNS side effects.

To be eligible, subjects must not be treated with CNS-active drugs for **5 half-lives of the respective drug (but at least 2 weeks) prior to V1**. The use of CNS-active drugs is forbidden or restricted until 24 hours after EOT (V7).

Drug Class	Examples	Forbidden / Restricted	Comment
Centrally Acting Anticholinergics and Antihistamines	OTC Histamine 1-Antihistamines, e.g.: Diphenhydramine HCl, Carbinoxamine, Dimenhydrinate, Triprolidine HCl Hydroxyzine	F	
Antihistamines	Sedating Non-sedating (loratidine, fexofenadine)	F R	Non-sedating antihistamines may be used maximum twice weekly for allergic symptoms.
Psychotropics	Stimulants: Amphetamines Modafinil, armodafinil Methylphenidate	F	
	Antidepressants	F	
	Antipsychotics, including depot neuroleptics	F	
	Anxiolytics, e.g.: Lorazepam Alprazolam Buspirone	F	
	Sleep medications, e.g.: Prescribed zolpidem and other sleep medicines, suvorexant, ramelteon and OTC	F	
	MAOIs	F	
	Melatonin	F	
	Mood stabilizers, e.g.: Lamotrigine Gabapentin Lithium Oxcarbazepine Carbamazepine	F	

	Valproic acid		
	Narcotics	R	Use of narcotics for pain relief must be avoided if there are effective alternative medications (such as NSAIDs)
	Centrally acting muscle relaxants with psychotropic effects e.g., Methocarbamol	R	Use of centrally acting muscle relaxants must be avoided if there are effective alternative medications (such as NSAIDs)
	Herbal preparations with possible psychotropic effects, e.g., St Johns Wort, valerian	F	
	Tryptophan	F	
Anticonvulsants	Barbiturates Benzodiazepines GABA analogs Hydantoins Phenyltriazines (e.g, lamotrigine) Succinimides (e.g., Ethosuximide)	F	
Other	Warfarin, Heparin, Ticlopidine	F	
	Isotrenitoin	F	
	Systemic glucocorticoids	F	
	Diet Pills (prescription and OTC)	F	
	Pseudoephedrine	R	May only be used before 14.00, and no more than twice a week. Dosage is limited to 30 mg of active ingredient in each tablet. Extended release formulations are forbidden.

GABA = gamma-aminobutyric acid; MAOI = monoamine oxidase inhibitor; NSAID = nonsteroidal anti-inflammatory drug; OTC = over-the-counter.

2. Non-exhaustive list of forbidden concomitant medications and diets due to potential drug interactions with CYP3A4 (moderate and strong inhibitors, inducers and sensitive substrates), with P-gP substrates, with BCRP substrates, and with CYP2B6 substrates.

Those medications must be discontinued no later than **1 week prior to V1** and are forbidden until 24 hours after EOT (V6).

CYP3A4 moderate and strong inhibitors and CYP3A4 inducers:

Inhibitors of CYP3A4	Inducers of CYP3A4
HIV antivirals: atazanavir, boceprevir, cobicistat, darunavir, delaviridine, fosamprenavir, indinavir, lopinavir, nelfinavir, ritonavir, saquinavir, telaprevir	HIV antivirals: efavirenz, etravirine, nevirapine
Antibiotics: ciprofloxacin, clarithromycin, erythromycin, norfloxacin, quinupristin, telithromycin, troleandomycin,	Antibiotics: nafcillin, rifabutin, rifampin
Antifungal: fluconazole, itraconazole, ketoconazole, posaconazole, voriconazole	
CNS-active: fluvoxamine, nefazodone	CNS-active: carbamazepine, fenobarbital, modafinil, phenytion, St John's Wort
Cardiovascular: amiodarone, diltiazem, dronedarone, mibefradil, verapamil	Cardiovascular: bosentan
	Hypoglycemics: pioglitazone, troglitazone
Aprepitant, conivaptant, cimetidine, imatinib	
Grapefruit and grapefruit juice	

[figure not shown]
CYP3A4 substrates: alfentanil, apixaban, budesonide, buspirone, cisapride, crizotinib, cyclosporine, darifenacin, dihydroergotamine, domperidone, dronedarone, erlotinib, ergotamine, ethinylestradiol, erythromycin, felodipine, fentanyl, halofantrine, ketamine, lovastatin, lurasidone, maraviroc, midazolam, nifedipine, nisoldipine, oxycodone, quetiapine, saquinavir, sildenafil, simvastatin, sirolimus, tacrolimus, terfenadine, ticagrelor, tipranavir/ritonavir, tolvaptan, triazolam, vardenafil, verapamil.

P-gP substrates: aliskiren, ambrisentan, colchicine, dabigatran etexilate, digoxin, everolimus, fexofenadine, imatinib, lapatinib, maraviroc, nilotinib, posaconazole, ranolazine, saxagliptin, sirolimus, sitagliptin, talinolol, tolvaptan, topotecan.

[figure not shown]
BCRP substrates: imatinib, irinotecan, lapatinib, methotrexate, mitoxantrone, rosuvastatin, sulfasalazine, topotecan.

CYP2B6 substrates: bupropion, cyclophosphamide, efavirenz, irinotecan, ketamine, promethazine, propofol, selegiline, valproic acid.

[figure not shown]

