1.4 Summary of known and potential risks and benefits

1.4.1 ACT-541468

Based on the mechanism of action of ACT-541468, and current nonclinical data and data collected in Phase 1 studies in healthy adult and elderly subjects, a fast effect on sleep induction and a sustained effect on sleep maintenance are anticipated. Suvorexant, a compound with a similar mechanism of action, has been demonstrated to be efficacious in the treatment of insomnia without evidence of physical dependence or withdrawal symptoms after discontinuation of suvorexant.

ACT-541468 crosses the blood–brain barrier and decreases wakefulness in rats and dogs, is associated with a short sleep latency, and increases sleep efficacy following oral administration. In particular, it shows a shorter latency to non-REM sleep and better sleep efficacy than suvorexant in rats and shorter duration of sleep in dogs. REM and non-REM sleep are prolonged proportionately in rats and dogs, thus decreasing wakefulness while preserving natural sleep architecture.

This study will be the first study with the compound in elderly subjects with insomnia disorder. In humans, clear and consistent CNS-depressant effects were observed at the morning dose of 25 mg in healthy young adults and elderly subjects. An effect was also seen on the most sensitive PD parameter, saccadic peak velocity, after morning single dose administration of 15 mg ACT-541468 in healthy elderly subjects. There were no relevant differences between PD effects measured on Day 1 and Day 5. In the

Phase 1 studies, no next-day residual effects were observed after multiple evening dose administration both in healthy young and elderly subjects at 25 mg.

The most frequently observed adverse drug reactions reported in the conducted studies involving approximately 110 healthy subjects exposed to ACT-541468 include headache, somnolence, fatigue and dizziness. Elderly subjects reported fewer AEs than young adults in Phase 1 studies at the equivalent dose.

The results of the ACT-078-103 study have shown that ACT-541468 metabolism is mainly dependent on CYP3A4; co-administration of ACT-541468 and strong or moderate CYP3A4 inhibitors must be avoided.

Considering both the mode of action of DORA and common adverse reactions associated with the use of sleep medications, potential risks include:

- Induction of next-day somnolence, which is associated with increased risk of impaired alertness and motor coordination.
- Narcolepsy-like events.

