3.1.1.2 Double-blind treatment phase

The double-blind **treatment phase** starts with the first dose of study treatment in the first evening of the Randomization visit (V3) and ends in the second morning of V7. It consists of five **treatment periods**, each consisting of two consecutive PSG nights on the assigned study treatment followed by a 5- to 12-day washout.

The **End of Treatment (EOT)** is reached in the second morning of V7, after the last dose of double-blind treatment and after all morning assessments have been performed.

The **safety Follow-up phase** starts after the EOT and lasts at least 30 days (i.e., until the second follow-up telephone call). A first telephone call is done 5 days (+ 7 days) after EOT to collect TEAEs from the last study treatment dose.

[figure not shown]
The **End of Study (EOS)** for a single subject is defined as the date of the 30-day follow-up telephone call. If a subject withdraws consent and does not wish to participate in the study any longer, EOS is the date of consent withdrawal for this subject. If a subject is declared lost to follow-up [see also Section 8.2], EOS is the date of last successful contact for this subject.

Unscheduled visits are allowed to take place anytime during the study, in which case study-related information will be collected.

The visit schedule and protocol-mandated procedures will be performed according to the table of assessments [Table 3] and are described in Section 7.

The overall study design is depicted in [Figure 1].

Figure 1 Study design

V = visit; — polysomnographic (PSG) nights; D = dose; P = placebo.

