14. Any known factor or disease that might interfere with treatment compliance, study conduct or interpretation of the results such as history of non-compliance to medical

- regimen, psychiatric disease, or neurological disorders which may impact sleep, motor performance, or cognition, including Parkinson disease, predementia, dementia, other neurodegenerative disorders, and stroke (V1).
15. Treatment with another investigational drug within 1 month prior to V1.
 16. Known hypersensitivity or contraindication to drugs of the same class of the study treatment or to any excipients of the study drug formulation (V1).
 17. Treatment with prohibited CNS active drugs [as defined in [Appendix 4](#)] for 5 half-lives of the respective drug (but at least 2 weeks) prior to V1 and until 24 hours after EOT, including over-the-counter (OTC) medication and herbal medicines.
 18. CBT within one month prior to V1.
 19. Treatment with moderate to strong CYP3A4 inhibitors, CYP3A4 inducers, sensitive CYP3A4 substrates, P-glycoprotein 1 (P-gP) substrates, Breast Cancer Resistance Protein (BCRP) substrates, and CYP2B6 substrates [as defined in [Appendix 4](#)] within 1 week prior to V1 until 24 h after EOT.
 20. Consumption of grapefruit and grapefruit juice within 1 week prior to V1.
 21. Diagnosis of alcohol or drug abuse or dependence within 2 years prior to the screening visit or inability to refrain from drinking alcohol for at least 3 consecutive days (V1).
 22. Positive drug test (for benzodiazepines, barbiturates, cannabinoids, opiates, amphetamines, or cocaine) or presence of alcohol in exhaled breath as detected by a breathalyzer test (V1,V2).
 23. Heavy tobacco use (≥ 10 cigarettes per day), and/ or inability to refrain from smoking for at least 14 hours during the night (V1).
 24. Apnea/hypopnea index (AHI) ≥ 15 /h on the first PSG screening night according to the American Academy of Sleep Medicine (AASM) criteria [[Meoli 2001](#), [CMS 2008](#)] (V2).
 25. Apnea or hypopnea event (according to AASM criteria [[Meoli 2001](#), [CMS 2008](#)]) associated with oxygen saturation by pulse oximetry (SpO_2) $< 80\%$ on the first PSG screening night (V2).
 26. Periodic limb movement with arousal index (PLMAI) ≥ 15 /h on the first PSG screening night (V2).

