5.2.4 Forbidden concomitant therapy

Patients must not be withdrawn from medically necessary therapies in order to participate in the study. They must rather be considered as non-eligible to the study, both due to their medical condition and due to their requirement for these therapies. Several forbidden

therapies are associated with excluded medical disorders (e.g., cardiovascular disease, stroke).

The following therapies are forbidden during the study:

- Treatment with another investigational drug until the end of the safety follow-up phase.
- Prohibited CNS-active medications, including OTC medications and herbal medicines, until 24 hours after EOT [see [Appendix 4](#)].
- Treatment with moderate to strong CYP3A4 inhibitors, CYP3A4 inducers, sensitive CYP3A4 substrates (i.e., have low bioavailability due to a marked first-pass effect), P-gp substrates, BCRP substrates and CYP2B6 substrates until 24 hours after EOT [see [Appendix 4](#)].
- CBT and other psychological therapies, excluding common advice related to sleep hygiene, until 24 hours after EOT.

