**Table 1 Latin square design sequences**

[figure not shown]
		Treatment period (double-blind)				
		1	2	3	4	5
Sequence	1	Dose 4	Dose 2	Dose 3	Dose 1	Placebo
	2	Dose 2	Placebo	Dose 4	Dose 3	Dose 1
	3	Dose 3	Dose 1	Dose 2	Placebo	Dose 4
	4	Placebo	Dose 4	Dose 1	Dose 2	Dose 3
	5	Dose 1	Dose 3	Placebo	Dose 4	Dose 2

The study design is shown in [Figure 1](#). Single-blind placebo (two capsules of ACT-541468-matching placebo) is administered at V2 (run-in) and double-blind study treatment is administered at V3, V4, V5, V6 and V7. To keep the blind, a placebo capsule matching ACT-541468 will be administered concomitantly with one capsule of ACT-541468 for the 5, 10, and 25 mg doses, while for the 50 mg dose, two capsules of ACT-541468 25 mg will be administered. The double-blind treatment phase consists of five treatment periods starting with the first dose of study treatment in the first evening of

the randomization visit (V3) and ending in the second morning of V7. Each treatment period consists of two consecutive PSG nights on the assigned study treatment which is directly followed by a 5- to 12-day washout period. The End-of-Treatment is reached in the second morning of V7 after the last dose of double-blind treatment and after all morning assessments have been performed.

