## **13 GENERAL DEFINITIONS AND DERIVATIONS**

### **13.1 Treatment start and end dates**

Double-blind study treatment start and end dates are the earliest and latest dates, respectively, of dose intake recorded on the ‘Study Double-blind Treatment Log’ page.

Run-in single-blind placebo treatment start date (i.e., the start date of the single-blind placebo treatment period), is the earliest date of dose intake (i.e., date of capsules administered) recorded on the ‘Study Single Blind Treatment Dispensing & Accountability’ page at V2.

Treatment period 1 start date is the earliest date of dose intake (i.e., date of capsules administered) recorded for Visit 3 on the ‘Study Double Blind Treatment Dispensing & Accountability’ page.

Treatment period 2 start date is the earliest date of dose intake (i.e., date of capsules administered) recorded for Visit 4 on the ‘Study Double Blind Treatment Dispensing & Accountability’ page.

Treatment period 3 start date is the earliest date of dose intake (i.e., date of capsules administered) recorded for Visit 5 on the ‘Study Double Blind Treatment Dispensing & Accountability’ page.

Treatment period 4 start date is the earliest date of dose intake (i.e., date of capsules administered) recorded for Visit 6 on the ‘Study Double Blind Treatment Dispensing & Accountability’ page.

Treatment period 5 start date is the earliest date of dose intake (i.e., date of capsules administered) recorded for Visit 7 on the ‘Study Double Blind Treatment Dispensing & Accountability’ page.

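### Appendix 4 part 2 labels End of Treatment as V6 when it ends the ban on interacting drugs, but the protocol and SAP define End of Treatment at V7; the label needs reconciling (minor)

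*Protocol*

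**What the plan says.** Part 2 of Protocol Appendix 4 lists drugs with interaction potential: moderate and strong CYP3A4 inhibitors, CYP3A4 inducers, sensitive CYP3A4 substrates, and P-gP, BCRP and CYP2B6 substrates. It states that they "are forbidden until 24 hours after EOT (V6".

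Section 3.1.1.2 says that EOT "is reached in the second morning of V7, after the last dose of double-blind treatment". The synopsis agrees, and SAP Section 2 repeats it: "The End-of-Treatment is reached in the second morning of V7 after the last dose of double-blind treatment".

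Part 1 of Appendix 4, on a different group of drugs, has: "The use of CNS-active drugs is forbidden or restricted until 24 hours after EOT (V7".

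The body of the protocol states the interacting-drug ban twice without naming a visit for its end. Section 5.2.4 forbids these drugs, including "P-gp substrates, BCRP substrates and CYP2B6 substrates until 24 hours after EOT". Exclusion criterion 19 in Section 4.4 applies "within 1 week prior to V1 until 24 h after EOT". Both refer to Appendix 4 for the drugs concerned.

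**The concern.** Two visits are attached to one milestone, and the difference between them is a whole treatment period. Appendix 4 is where the body text sends sites for the drug list. It is also the only place where the end of this particular ban is tied to a visit number. Someone working from that page and planning by visit could conclude that the restriction lapses after V6, while dosing at V7 is still to come.

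The restriction has a stated pharmacological reason. Section 1.4.1 reports that metabolism depends mainly on CYP3A4 and that "co-administration of ACT-541468 and strong or moderate CYP3A4 inhibitors must be avoided". If a subject started such a drug between V6 and V7, these could be affected for that subject in period 5:

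- drug exposure and next-day safety findings;
- the concentration 9 to 10 hours after dosing, which feeds the PK summaries and the exposure-safety plots (SAP Sections 10.6 and 10.7);
- whether the use counts as a protocol deviation, which bears on the deviation tables (SAP Section 6.3) and possibly on per-protocol membership (SAP Section 5.5).

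**Working it through.** **Step 1. The passages side by side.**

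| Place | Subject matter | Milestone | Visit named |
|---|---|---|---|
| Protocol Appendix 4, part 2 | Interacting drugs | 24 h after EOT | V6 |
| Protocol Section 5.2.4 | Interacting drugs | 24 h after EOT | none |
| Protocol Section 4.4, criterion 19 | Interacting drugs | 24 h after EOT | none |
| Protocol Appendix 4, part 1 | CNS-active drugs | 24 h after EOT | V7 |
| Protocol synopsis and Section 3.1.1.2; SAP Section 2 | Definition of EOT | EOT | V7 |

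The direct counterparts of the appendix line are Section 5.2.4 and criterion 19, read with the definition in Section 3.1.1.2. Part 1 of the appendix is corroboration only, because it concerns other drugs.

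**Step 2. Which visit fits the protocol's own figure.** Section 3.1.2 gives 30 to 58 days for the double-blind phase. Each period has 2 treatment days, with 5 to 12 days between successive periods.

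- Length = (periods × 2) + (washouts before the last period × 5 to 12).
- EOT at V7 (five periods, four washouts): 5×2 + 4×5 = 30; 5×2 + 4×12 = 58. This reproduces the stated range.
- EOT at V6 (four periods, three washouts): 4×2 + 3×5 = 23; 4×2 + 3×12 = 44. This does not.

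**Step 3. What the V6 label would leave uncovered.** SAP Section 13.1 says "Treatment period 5 start date is the earliest date of dose intake (i.e., date of capsules administered) recorded for Visit 7", so V6 is period 4. Protocol Section 7.1 puts each treatment visit 5 to 12 days after the previous one. A ban ending 24 hours after V6 would stop about 5 − 1 = 4 to 12 − 1 = 11 days before the first dose at V7.

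**Step 4. What the defined term gives.** If EOT in the appendix line carries its defined meaning, the ban runs to 24 hours after the second morning of V7, and all five periods are covered.

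The conflict is therefore between a parenthetical label and the defined term inside the same sentence.

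**The case against.** The strongest answer is that EOT is the controlling term and is defined consistently. On that view the V6 in parentheses is a slip that cannot override the definition. The body text states the ban to 24 hours after EOT with no conflicting label, and Section 1.4.1 says without a time limit that moderate and strong CYP3A4 inhibitors are to be avoided with the study drug. This stands, and it is why the point is minor.

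Other safeguards narrow the gap. Section 5.2.3 discourages new medications. Section 7.2 lists the recording of concomitant medications before study drug intake in the recommended evening order, and site staff administer the doses. Grapefruit is banned separately in Section 5.2.5. Some listed drugs, such as carbamazepine, modafinil and St John's Wort, also appear in part 1 of the appendix, which is labelled V7.

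These safeguards do not remove the conflict. Several listed anti-infectives, such as clarithromycin, erythromycin and fluconazole, appear only in part 2. Recording a medication does not flag it as forbidden if the reader has taken the label at face value.

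A reader might also infer that one fifth of all dosing is compromised. Period 5 is one of five, and each treatment is planned for 50/5 = 10 subjects at V7, including 50 mg in sequence 3. The documents do not support that inference. Those figures count everyone due to be dosed at V7. The subjects at issue are only those who start a listed drug after the V6 label would have released it, at a site that follows the label over the definition.

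**Conclusion.** The inconsistency is real and in current text, and it is minor. It is a labelling conflict, not a design choice: nothing in the documents suggests that anyone meant the ban to stop before the last treatment period. It would be going too far to say that the protocol permits CYP3A4 inhibitors in period 5, because that requires the parenthesis to prevail over a term defined in the synopsis, Section 3.1.1.2 and the SAP.

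The possible effect is confined to individual subjects who start a listed drug between V6 and V7. Their number cannot be estimated, since the documents give no rate, and nothing shows that any site acted on the label. Sample size, alpha and the primary test are not touched. The finding rests on reading the V6 as printed in the current appendix.

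**What to change.** The sponsor should reconcile the visit label in Appendix 4, part 2, with the EOT definition in Section 3.1.1.2, with Section 5.2.4 and exclusion criterion 19, and with the label in Appendix 4, part 1, and tell sites the outcome. The protocol deviation document to which SAP Section 5.5 refers should use the same reconciled end point, so that use between V6 and V7 is classified consistently. No clinical rule is proposed here.

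The cost is one label in the appendix, made through a written amendment as Section 12.6 requires for any protocol change, and a short note to sites. No analysis has to change.

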Appendix 5 Digit Symbol Substitution Test[®]

[figure not shown]
Appendix 6 Insomnia Severity Index[®]

[figure not shown]
Appendix 7 Sheehan Disability Scale®

[figure not shown]

Appendix 8 Karolinska Sleepiness Scale

Appendix 9 Sleep diary

Appendix 10 Summary table of efficacy variables

Objectives	Variables	Endpoints	
Sleep maintenance	WASO	Absolute change from Baseline ^a to Days 1 and 2 ^b	Primary
	WASO overnight	Absolute change from Baseline ^a to Days 1 and 2 ^b by hour of the night and by quarter of the night	Exploratory
Sleep initiation	LPS	Absolute change from Baseline ^a to Days 1 and 2 ^b	Secondary
	sLSO	Absolute change from Baseline ^c to Days 1 and 2 ^d	Exploratory
Total sleep time	TST	Absolute change from Baseline ^a to Days 1 and 2 ^b	Exploratory
	sTST	Absolute change from Baseline ^c to Days 1 and 2 ^d	
Sleep quality	VAS	Absolute change from Baseline ^c to Days 1 and 2 ^d	Exploratory
Sleep architecture	Sleep stages duration	Mean ^c duration and mean percent of TST of each sleep stage (S1, S2, SWS and REM) for the whole night, and for each quarter of the night.	Exploratory
	Sleep stages latency	Mean ^c latency to each sleep stage (S1, S2, SWS, and REM).	
Sleep continuity	Shifts between sleep stages	Mean ^c number and frequency of shifts from S2, SWS or REM to S1 or wake for the whole night.	Exploratory
	Wake time during sleep	Mean ^c wake time during sleep: time spent in epochs scored as wake between LPS and last epoch not scored wake for the whole night.	
	Awakenings	Mean ^c frequency of awakenings: number of awakenings between first epoch and last epoch not scored wake for the whole night, by hour of the night and by quarter of the night.	
	sNA	Absolute Change from Baseline ^c to Days 1 and 2 ^d in self-reported number of awakenings	
Sleep efficiency	SE	Absolute change from Baseline ^a to Days 1 and 2 ^b	Exploratory

Next-day performance	VAS	Absolute change from Baseline ^c to Days 1 and 2 ^d	Exploratory
----------------------	-----	---	-------------

Note: a 'Baseline' is the mean of the two PSG nights during run-in period (V2), b 'Days 1 and 2' is the mean of the corresponding two PSG treatment nights for a given treatment period, c 'Baseline' is the mean value of the sleep diary entries during run-in period (V2), d 'Days 1 and 2' is the mean value of the corresponding sleep diary entries for a given treatment period, e 'Mean' calculated based on two PSG nights value for a given treatment period.

LPS = latency to persistent sleep; PSG = polysomnography; REM = rapid eye movement; SE = sleep efficiency; sLSO = subjective latency to sleep onset; sNA = self-reported number of awakenings; sTST = subjective total sleep time; SWS = slow-wave sleep; TST = total sleep time; VAS = visual analog scale; WASO = wake after sleep onset.
